Redesigning Pediatric Primary Care Obesity Treatment: Virtual House Calls

NCT06078774

09.19.2023

PROTOCOL

The Virtual HouseCalls model is designed to augment existing primary care approaches for management of childhood obesity preventing progression to severe obesity. This approach will leverage existing, widely accessible telehealth technologies to improve reach to populations with disparities in obesity prevalence. The goal is to develop an evidence-based intervention that could be widely integrated into pediatric patient-centered medical homes. The study question is to establish the feasibility of this intervention and support a future application.

STUDY AIMs:

Aim 1: To test the feasibility and preliminary efficacy of the Virtual HouseCalls intervention.

Aim 2: To test the preliminary efficacy of Virtual HouseCalls on BMI and secondary outcomes of parenting, child diet and physical activity, sleep and home food environment.

RECRUITMENT:

We plan to recruit 50 parent-child dyads using established strategies. Eligible families will be invited to an informed consent discussion virtually (Zoom) or in person, in which study procedures will be detailed, eligibility confirmed, and consent/assent obtained. Consented participants will receive detailed instructions for completing baseline assessments.

INTERVENTION:

Parents will attend a 60-minute orientation at the start of the intervention to review study logistics: telehealth visit setup, prioritizing modules, and setting study expectations. Week 1, dyads will attend a meeting with their health coach to launch the program that will last up to 60 minutes. Dyads will then attend weekly 30-minute sessions with their coach weeks 2-12 (intensive phase) and bi-weekly 30-minute sessions with their coach weeks 13-24 (maintenance phase). During the intensive phase, all dyads will receive the same 12 modules; however, during the maintenance phase, dyads will select the topics of their choice for each session (see Session Outline document). Sessions follow a behavior therapy approach, including guided goal-setting, self-monitoring, identifying barriers and solutions, contingency management, stimulus control, dealing with setbacks, maintenance and relapse prevention. Weight is assessed weekly by coaches, with MI-consistent, autonomy-supportive feedback provided. Weeks 2-4, parents will have one, 60-minute visit with their coach; this will occur again during weeks 12-15. These individual parent sessions will focus on ways to support their child's weight management. Dyads will also be sent weekly exercise videos (1x/week for 30 min) and be encouraged to participate in them. All sessions will be conducted virtually utilizing Zoom or EPIC.

Participants will be provided scales to be used for weekly self-weighing and will be provided guidance on self-regulation by their coach.

ASSESSMENTS:

All assessments will occur at baseline, 3-, and 6-months (primary) unless otherwise noted.

CHILD:

- Trained staff measure height and weight to the nearest 0.1cm and 0.1kg using a precision stadiometer and digital scale, respectively. BMI will be calculated (kg/m²).
- Children will complete the following psychosocial measures via REDCap:
 - The Authoritative Parenting Index (Jackson et al, 1998) will assess child report of parenting style
 - A subset of questions from Project Eat (Neumark-Sztainer, 2002 et al) will be used to assess eating and weight-related habits
 - 2 item physical activity scale (Prochaska et al., 2001) assessing weekly engagement in physical activity.
 - Children's Eating Disorder Examination Questionnaire (Kliem et al, 2017) will assess eating disorders.
- Children will complete the Automated Self-Administered 24-Hour (ASA24®) from NCI that assesses dietary intake.

PARENT:

- Trained staff measure height and weight to the nearest 0.1cm and 0.1kg using a precision stadiometer and digital scale, respectively. BMI will be calculated (kg/m²).

- Parents will complete the following psychosocial measures via REDCap:
 - Demographics (baseline only) will assess household income, family structure, weight management treatments
 - Food insecurity (USDA, 2012) will be assessed
 - Home Food Inventory (Fulkerson et al, 2008) will assess what food is available in the home
 - The Standardized Screening Tool for Health (Billionix et al, 2017) will assess health-related social needs that negatively impact health
 - Parenting Style Dimension Questionnaire short version, authoritative parenting subscale (Robinson et al, 2001) will assess parent report of parenting style
 - 2 item physical activity scale (Prochaska et al., 2001) assessing weekly engagement in physical activity.
 - A subset of questions from the Family Mealtime Environment (Berge et al 2016) questionnaire will assess the household environment during family meals
 - Modified NHANES sleep time questions (Centers for Disease Control and Prevention (CDC). National Center for Health Statistics (NCHS). National Health and Nutrition Examination Survey Data. Hyattsville, MD: U.S. Department of Health and Human Services, Centers for Disease Control and Prevention) will assess

Attendance and adherence will be monitored. At the 6-month assessment only, all participants will complete an Exit Survey assessing: intervention likes/dislikes; perceived benefits and barriers to implementing intervention goals; overall satisfaction; and suggestions for improvement.

STATISTICAL ANALYSIS:

A proposed sample size of 50 dyads, or parent-child pairs, will allow investigators to establish feasibility and proof of concept. Primary outcomes will be determined with percentage calculations ($[\text{actual}/\text{target}]*100$) to determine percent recruited, percent retained, and percent satisfied. Secondary outcomes will be examined using descriptive statistics to calculate scale means and standard deviations at assessment time points. Paired samples t-tests will be used to examine changes in secondary outcomes over the course of the 6-month intervention.

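### Both aims claim a test of preliminary efficacy, but uncontrolled 6-month change cannot be attributed to the intervention, and the child BMI metric and its analysis are not settled

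*Combined protocol and SAP*

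**What the plan says.** **Aims.** Under STUDY AIMs, Aim 1 is "To test the feasibility and preliminary efficacy of the Virtual HouseCalls intervention" and Aim 2 is "To test the preliminary efficacy of Virtual HouseCalls on BMI and secondary outcomes of parenting, child diet and physical activity", followed by sleep and the home food environment. The opening PROTOCOL text is narrower: "The study question is to establish the feasibility of this intervention and support a future application".

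**Design.** No control group, allocation or external comparison is described. RECRUITMENT plans 50 dyads with no division into groups. INTERVENTION says that in the intensive phase "all dyads will receive the same 12 modules". The protocol does not use the term single-arm; that is an inference from these passages.

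**Other care.** The opening text says "The Virtual HouseCalls model is designed to augment existing primary care approaches for management of childhood obesity". Other weight treatment appears in the parent list of ASSESSMENTS: "Demographics (baseline only) will assess household income, family structure, weight management treatments". No later record of it is listed.

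**Child BMI.** ASSESSMENTS (CHILD) has staff measure height and weight and gives BMI in kg/m². The parent entry has the same formula. No z-score, centile or other growth reference is mentioned.

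**Analysis.** STATISTICAL ANALYSIS makes the percentages recruited, retained and satisfied the primary outcomes. It then says "Secondary outcomes will be examined using descriptive statistics to calculate scale means and standard deviations at assessment time points", and assigns paired t-tests to 6-month change in the secondary outcomes. No success rule and no limit on attribution is stated.

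**The concern.** A paired t-test asks whether mean change is zero. To read the answer as efficacy, zero must be the change expected without the intervention. Nothing in the design supports that. Families also receive ordinary primary care, time passes, a sample recruited for a high value can regress to the mean, and most of the behavioural outcomes are self-reported by coached families.

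For child BMI there is a further problem. In growing children, zero change in raw kg/m² is not the no-effect value, so this metric can mimic benefit or hide it.

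The study is meant to support a future application and to show proof of concept. With no success rule, a significant or non-significant change in BMI could be reported there as evidence for or against efficacy. The design supports neither statement.

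**Working it through.** The plan has no efficacy calculation to reproduce. It gives no alpha, power, effect size, SD or dropout, and it rests the 50 dyads on feasibility and proof of concept. The check therefore has one textual step and three illustrations. Every numerical input other than 50 dyads is an assumption.

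**1. Aims against analysis.**

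| Item | Aims | Analysis |
|---|---|---|
| Claim | Tests preliminary efficacy | Examines change within participants |
| BMI | Named in Aim 2, apart from the secondary outcomes | Not among the primary percentages; t-tests go to secondary outcomes only |
| Whose BMI | Not stated | Child and parent BMI are both measured |
| Child metric | BMI | kg/m² only |

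The aims claim more than the analysis delivers. Read strictly, BMI has no assigned analysis.

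**2. Growth and raw BMI.** With weight w, height h and growth g, the weight gain that leaves BMI unchanged is w × ((h + g)/h)² − w.

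For 60 kg, 140 cm and 3 cm of growth:
- Starting BMI is 60/1.40² = 30.61.
- Break-even gain is 60 × (143/140)² − 60 = 2.60 kg.
- BMI after 6 months is (60 + gain)/1.43², so:

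| Weight gain (kg) | 0 | 2 | 3 | 5 |
|---|---|---|---|---|
| Change in BMI (kg/m²) | -1.27 | -0.29 | +0.20 | +1.17 |

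Break-even gain for other assumed sizes (kg):

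| Child | +2 cm | +3 cm | +4 cm |
|---|---|---|---|
| 45 kg, 130 cm | 1.40 | 2.10 | 2.81 |
| 60 kg, 140 cm | 1.73 | 2.60 | 3.48 |
| 75 kg, 155 cm | 1.95 | 2.93 | 3.92 |

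The sign depends on expected growth and weight gain. The documents give neither these nor child age, so the direction cannot be fixed.

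**3. Drift with no intervention effect.** For a two-sided 5% paired t-test on n pairs, with mean drift d in SDs of change, the chance of p < 0.05 comes from the noncentral t distribution with n − 1 degrees of freedom and noncentrality d√n. Take n = 50 (no loss) or n = 40 (20% loss).

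| Drift d (either direction) | n = 40 | n = 50 |
|---|---|---|
| 0 | 5% | 5% |
| 0.1 | 9.5% | 10.7% |
| 0.2 | 23.5% | 28.4% |
| 0.3 | 45.7% | 54.8% |
| 0.5 | 86.9% | 93.4% |

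**4. Drift with a true effect.** Take a true fall of 0.3 SD at n = 40. The chance of a significant fall is:
- no drift: 46%;
- drift of -0.2 SD (net -0.5): 87%;
- drift of +0.2 SD (net -0.1): 9%.

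Drift can thus create a result or hide one.

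**The case against.** The strongest defence is that this is openly a feasibility pilot. The study question, the primary outcomes and the sample-size rationale all concern feasibility or proof of concept. The aims say preliminary, and the analysis text speaks only of examining change. That stands, and it limits the point to the aims' wording and the reading of the BMI and secondary results. It does not remove the point: preliminary describes the strength of evidence, and does not turn uncontrolled change into an estimate of effect.

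A second objection is that the kg/m² sentence is a measurement rule, identical for parents, and is also the first step towards any centile or z-score. That stands too. A reader might infer that the plan commits to a t-test on raw child BMI. The documents do not say so, because they assign BMI no clear analysis. What can be said is that raw kg/m² is the only metric given.

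Third, the drift figures have no anchor in the documents. This also stands. They show how the test behaves, not how large the problem is here.

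Finally, asking about other weight treatment again at 3 and 6 months would not by itself isolate an effect without a comparator. The baseline-only question therefore illustrates the limit on attribution and is not its cause.

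**Conclusion.** The concern holds in limited form. Both aims claim a test of preliminary efficacy that an uncontrolled pre-post comparison cannot provide. Separately, the child BMI metric takes no account of growth, and the analysis of BMI is not clearly assigned. The first conclusion rests on the inference that there is no comparator, since none is described.

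The documents do not support three stronger readings that a reader might draw:
- **That the study's primary results or sample size are undermined.** The feasibility percentages and the 50 dyads do not depend on BMI.
- **That raw BMI is biased towards showing benefit.** The same 3 cm of growth goes with a fall or a rise, depending on weight gain.
- **That the false-positive risk is as high as 93%.** That figure needs an assumed drift of 0.5 SD, no dropout and a two-sided 5% level. None of these is in the documents.

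The correction should be made before results are reported, but it does not call for a redesign.

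**What to change.** 1. **Aims.** Limit Aim 1 to feasibility. Reword Aim 2 to *estimate within-participant change* in BMI and the other outcomes. Add a sentence that change cannot be attributed to the intervention, given growth, time trends, regression to the mean, other care and self-report.
2. **Child BMI.** State that child BMI is analysed as 6-month change in one age- and sex-referenced metric, with the metric and its growth reference named before analysis. BMI as a percentage of the reference 95th centile is one example. Report it beside raw kg/m², with mean change, 95% CI and SD of change; the plan now specifies SDs only at the time points. The CI half-width, t(0.975, n − 1)/√n, would be 2.010/√50 = 0.28 SD of change with 50 pairs and 2.023/√40 = 0.32 SD with 40.

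**Cost.** Protocol wording and minor extra analysis, with no added arm, visit or participant. Height and weight are already measured. Age at visit and sex are also needed; the assessment lists name neither, so confirm that both are recorded. The referenced metric deals with growth only, and the limitation sentence must cover the rest. The downside is a more modest claim.

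### Child BMI is defined only in kg/m², with no age and sex reference, so its 6-month change mixes expected growth with any intervention effect

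*Combined protocol and SAP*

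**What the plan says.** Under ASSESSMENTS: CHILD, trained staff measure height and weight, and then "BMI will be calculated (kg/m²". ASSESSMENTS: PARENT uses the same sentence for the adults. The documents mention no z-score, percentile, percent of the 95th percentile, growth reference, or adjustment for age or sex.

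BMI carries an aim. Aim 2 in STUDY AIMs reads "To test the preliminary efficacy of Virtual HouseCalls on BMI and secondary outcomes of parenting", followed by other behavioural and home measures. The opening of the protocol adds: "The study question is to establish the feasibility of this intervention and support a future application". On timing, ASSESSMENTS states: "All assessments will occur at baseline, 3-, and 6-months (primary) unless otherwise noted".

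STATISTICAL ANALYSIS does not name BMI. The primary outcomes there are percentages "to determine percent recruited, percent retained, and percent satisfied". For the rest it says "Secondary outcomes will be examined using descriptive statistics to calculate scale means and standard deviations at assessment time points" and "Paired samples t-tests will be used to examine changes in secondary outcomes over the course of the 6-month intervention". The sample size is justified by feasibility: "A proposed sample size of 50 dyads, or parent-child pairs, will allow investigators to establish feasibility and proof of concept". The INTERVENTION section describes one group of dyads, all treated; no control arm or randomisation is described.

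**The concern.** In adults, BMI in kg/m² can reasonably be compared with itself six months later. In children, BMI changes with age, at a rate that depends on age and sex. The mean 6-month difference in raw BMI is therefore the sum of two parts: the change these children would have shown anyway as they grew, and whatever the intervention did. Both stated methods, means at each time point and paired t-tests, carry the two parts together.

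A control arm would absorb the growth part. Without one, the choice of metric is the simplest means left of reducing it. With raw BMI, part of the Aim 2 result would depend on the age and sex mix of the children who happen to enrol, and that result is likely to be used in support of the future application. Where BMI is rising with age, benefit would be masked; where it is falling, benefit would be mimicked.

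**Working it through.** **What can be reproduced.** The plan gives no power, alpha, SD or effect size for BMI, so there is no stated figure to check. What follows only shows scale.

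**Does the plan apply the t-test to child BMI?** STATISTICAL ANALYSIS assigns the t-test to secondary outcomes; Aim 2 mentions BMI and secondary outcomes side by side. Because the primary outcomes are the three feasibility percentages, the natural reading is that BMI falls among the secondary outcomes. That is an inference. On the other reading, no analysis of BMI is stated at all.

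**Inputs.**
- n = 50 children: from STATISTICAL ANALYSIS.
- n = 40 completers: assumed.
- SD of 6-month change in BMI, 1.0, 1.5 or 2.0 kg/m²: assumed.
- Expected growth in BMI over 6 months, g = 0.05 to 0.5 kg/m²: assumed.
- 95% confidence interval, two-sided: assumed.
- Growth is taken as the only time trend.

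**Step 1: precision.** Half-width of the interval = t(0.975, n−1) × SD / √n.
- n = 50: 2.010 × SD / 7.071 = 0.284, 0.426 and 0.568 kg/m² for SD 1.0, 1.5 and 2.0.
- n = 40: 2.023 × SD / 6.325 = 0.320, 0.480 and 0.640 kg/m².

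Some of the assumed growth values are as large as these half-widths or larger, so growth need not be lost in the noise.

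**Step 2: coverage of the intervention effect.** If the observed mean change estimates effect + g, the interval covers the effect with probability P(−t_c < T < t_c), where t_c = t(0.975, n−1) and T is noncentral t with n−1 degrees of freedom and noncentrality g√n / SD. The size of the effect drops out. Example: g = 0.2, SD = 1.0, n = 50 gives noncentrality 0.2 × 7.071 / 1.0 = 1.414 and coverage 0.716. With g = 0 coverage is 0.95.

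| g (kg/m²) | n = 50, SD 1.0 / 1.5 / 2.0 | n = 40, SD 1.0 / 1.5 / 2.0 |
|---|---|---|
| 0.05 | 0.936 / 0.944 / 0.947 | 0.939 / 0.945 / 0.947 |
| 0.1 | 0.893 / 0.925 / 0.936 | 0.905 / 0.930 / 0.939 |
| 0.2 | 0.716 / 0.848 / 0.893 | 0.765 / 0.870 / 0.905 |
| 0.3 | 0.452 / 0.716 / 0.820 | 0.543 / 0.765 / 0.848 |
| 0.5 | 0.066 / 0.363 / 0.590 | 0.131 / 0.462 / 0.662 |

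A downward trend of the same size gives the same coverage, with bias of the opposite sign.

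**Step 3: what it does to the t-test.** With n = 50, SD 1.0, a two-sided 5% test and an assumed true effect of −0.5 kg/m², the chance of a significant fall is 0.93 with no growth, 0.79 with g = 0.1 and 0.41 with g = 0.25. With no intervention effect, g = 0.25 gives a significant rise with probability 0.41, against a nominal 0.025.

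**Step 4: partial removal.** Suppose a referenced measure removes only half of the growth, so that g/2 replaces g, with the SD unchanged. At n = 50 and SD 1.0 / 1.5 / 2.0, coverage becomes:
- g = 0.1: 0.936 / 0.944 / 0.947
- g = 0.2: 0.893 / 0.925 / 0.936
- g = 0.3: 0.820 / 0.893 / 0.918
- g = 0.5: 0.590 / 0.789 / 0.861

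Half-removal helps in every row but does not restore 0.95.

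**The case against.** The strongest reply has four parts.

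1. The kg/m² line is a measurement instruction. A referenced measure is computed from that same BMI, so the plan may simply be silent on the analysis variable, and the link from BMI to the t-test is inferred. This is fair as to the text. But kg/m² is the only metric given, and following the plan as written leaves growth in the result. If BMI has no stated analysis, the same edit is needed.

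2. The numbers say little about this trial, since only n = 50 comes from the documents and coverage at that n runs from 0.066 to 0.947. This stands: the size is undetermined. The lowest figures also need the largest growth together with the smallest SD. Moreover, the plan promises no confidence interval and makes no explicit causal claim; the paired t-test is a valid test of mean BMI change. The issue is what that mean change represents when it is offered as preliminary efficacy.

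3. A single-arm study cannot attribute change whatever the metric. Regression to the mean, seasonality and other trends remain, and regression to the mean may act against growth, so the net direction of error is unknown. This too stands. It limits the benefit of the fix but gives no reason to keep a component that can be reduced at little cost.

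4. The study is mainly about feasibility, and a referenced measure could be derived later from stored height and weight. Both are true, provided date of birth and sex are held. What would be lost is a choice of metric made before the data are seen.

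**Conclusion.** The concern holds, as an inexpensive improvement to Aim 2. It is certain that no age- and sex-referenced child BMI measure is named and that no comparison group is described to take out growth. How much this matters is not known: under the stated assumptions the loss ranges from negligible (growth near 0.05 kg/m²) to severe (growth near 0.5 kg/m² with a small SD), and nothing in the documents narrows it. The conclusion rests on the children still growing over the 6 months and on BMI being analysed as a secondary outcome. The percentages recruited, retained and satisfied do not depend on it.

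**What to change.** 1. In ASSESSMENTS: CHILD, name one age- and sex-referenced BMI measure and its growth reference as the child weight outcome for Aim 2; percent of the age- and sex-specific 95th percentile is one example. Compute it from the height and weight already taken. Confirm that date of birth and sex are recorded, since the demographics line does not list them.
2. In STATISTICAL ANALYSIS, name this outcome, analyse its baseline-to-6-month change by paired t-test with a 95% confidence interval, and describe the result as uncontrolled pre-post change.
3. Keep raw BMI as a descriptive measure for the children, and leave the parents' BMI as it is.

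The cost is a few lines of text and a standard growth-reference calculation, with no added visits or measurements if date of birth and sex are held. The limitation to state is that expected growth is removed only to the extent that these children would otherwise track the reference curve; other time trends remain.

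### The child eating-disorder questionnaire has no clearly assigned analysis, and the group means and paired t-tests planned for secondary outcomes would probably miss marked worsening in a minority of children

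*Combined protocol and SAP*

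**What the plan says.** - **Measure.** ASSESSMENTS, CHILD lists the "Children's Eating Disorder Examination Questionnaire", completed by the child in REDCap, with the stated purpose of assessing eating disorders. No other timing is given for it, so the general rule applies: "All assessments will occur at baseline, 3-, and 6-months (primary) unless otherwise noted".
- **Nearby measure.** A subset of survey items "will be used to assess eating and weight-related habits". The items are not listed.
- **Weighing.** INTERVENTION states "Weight is assessed weekly by coaches" and "Participants will be provided scales to be used for weekly self-weighing". Neither sentence says whether child, parent or both are meant.
- **Outcomes.** Aim 2 covers BMI and "secondary outcomes of parenting, child diet and physical activity, sleep and home food environment". Eating-disorder symptoms are not on that list. The primary outcomes in STATISTICAL ANALYSIS are percentages recruited, retained and satisfied.
- **Analysis.** Secondary outcomes are examined using "descriptive statistics to calculate scale means and standard deviations at assessment time points", with paired t-tests for change over six months. The text gives no count of children who worsen, no cut-off, no display of individual scores and no safety outcome.

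**The concern.** A group mean suits an outcome on which most children are expected to move the same way. An adverse change in eating-disorder symptoms would more plausibly affect a few children, and a mean offsets their worsening against stability or small gains in the rest.

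The pilot is meant to support a later application for a programme that could be adopted widely in primary care. If the report shows only a mean and a p-value for this questionnaire, a later reader may take a non-significant change as reassurance that the data cannot give. If the questionnaire is not treated as a secondary outcome, the scores may not be reported at all. The same addition to the plan closes both gaps.

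**Working it through.** **Inputs from the documents.** "A proposed sample size of 50 dyads", so at most 50 children, assessed at three time points, with paired t-tests. The sample size rests on feasibility and proof of concept. No alpha, power, effect size, SD or dropout is given, so there is no calculation to reproduce.

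**Assumptions, not in the documents.** Two-sided 5% test; 40 or 50 children with paired scores; normally distributed change. Effects are in SDs of the change score unless stated otherwise. With a correlation r between visits, SD of change = √(2(1 − r)) baseline SDs: 1.00 at r = 0.5 and 0.775 at r = 0.7.

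**1. What the t-test can see.** For 80% power the noncentral t distribution needs a mean change of 0.40 SD with 50 children and 0.45 SD with 40.

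**2. What minority worsening does to the mean.** If a fraction p worsens by h and the rest change by g, the mean is p·h + (1 − p)·g.
- h = 1, g = 0: 0.1 × 1 = 0.10.
- h = 2, g = 0: 0.1 × 2 = 0.20.
- h = 1, g = −0.111: 0.1 − 0.9 × 0.111 = 0.
- h = 2, g = −0.222: 0.2 − 0.9 × 0.222 = 0.

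All lie well below 0.40. Simulated chance of a significant worsening:

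| 10% of children worsen by | Others | n = 40 | n = 50 |
|---|---|---|---|
| 1 SD | unchanged | about 8% | about 9% |
| 2 SD | unchanged | about 15% | about 18% |
| 1 SD | improve 0.11 SD | about 2% | about 2% |
| 2 SD | improve 0.22 SD | about 1% | about 1% |

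**3. Wider scenarios, in baseline SDs.** With 5 of 50 worse by 1 SD and 45 better by 0.2 SD, the mean is 0.1 − 0.9 × 0.2 = −0.08, an apparent improvement, and worsening is found in under 1% of trials. The most favourable case tried, 10 of 50 worse by 1.5 SD with the rest unchanged, gives 41% to 58%.

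**4. Would the planned SDs show it?** With 5 of 50 worse by 1 SD and r = 0.5, the SD of change rises from 1.00 to about 1.04 (others unchanged) or 1.06 (others improve 0.2 SD). That is too little to notice.

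**5. Would a count do better?** This depends on the threshold.
- *Threshold of 1 SD of change.* By noise alone 15.9% of unaffected children exceed it, and only 50% of those shifted by 1 SD do. In 40 children the expected count is 4 × 0.50 + 36 × 0.159 = 7.7 with harm, against 40 × 0.159 = 6.3 without. Detection is about 6% to 8%, no better than the t-test.
- *Worse of the 3- and 6-month scores, flagged at a rise of one baseline SD.* With no true change this flags about 10% of children at r = 0.8 and about 25% at r = 0.5, so 4 to 10 of 40.
- *Threshold of 1.96 SD of change, one visit.* Noise flags 2.5% of children in each direction, so 1 of 40 upward. If 4 of 40 shift by 2 SD, each exceeds the threshold with probability 0.516, and the expected count is 4 × 0.516 + 36 × 0.025 = 2.96. Calling harm at 4 or more (chance 1.7% under noise) detects it in about 33% of trials, against 15% for the t-test. If the rest improve by 0.22 SD, the figures are 22% against 1%. For a 1-SD shift the count again gains nothing (about 6%).

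**6. Precision of a reported count (exact 95% limits).** 4 of 40: 10% (2.8% to 23.7%). 5 of 50: 10% (3.3% to 21.8%). 0 of 40: upper limit 8.8%. 0 of 50: upper limit 7.1%. These limits describe observed changes, which include measurement noise.

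**The case against.** The best case for leaving the plan alone has four parts.

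*No stated aim depends on this.* The aims are feasibility and preliminary efficacy, and the plan promises no safety statement. That stands, and it is why the point is minor.

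*A count is not a clean harm detector.* Noise flags some children, a low threshold does no better than the t-test, and taking the worse of two visits inflates the count further. With one group there is no background rate for comparison. This also stands. A reader might infer that counting worsened children would show harm directly; step 5 shows that it would not. It limits the fix to a threshold above measurement noise, one visit at a time, reported in both directions.

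*The analysis is inferred.* A reader might conclude that the plan commits this questionnaire to a mean and t-test and nothing else. The documents assign those methods to secondary outcomes, and Aim 2 does not list this domain. The gap is then a missing analysis, which the same fix addresses.

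*The role is inferred.* A reader might call it the trial's only harm measure. No measure is labelled as one, and the unlisted items on eating and weight-related habits may overlap. Consent pages were removed from the public text and the Session Outline is not supplied, so how individual scores are handled cannot be judged here. The point concerns only the assessment and analysis text.

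**Conclusion.** The concern holds in a limited form. The one measure stated to assess eating disorders has either no assigned analysis or one that would probably miss marked worsening in a minority. With 10% of children worse by 1 to 2 SD of change, detection is about 8% to 18% if the rest are unchanged and about 1% to 2% if they improve slightly.

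A reader might go further and say that such harm could not be seen at all. The figures do not support that: detection reaches 41% to 58% when 20% of children worsen by 1.5 baseline SD and nobody else changes.

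All these figures rest on assumed proportions, shifts, correlations, follow-up numbers and normality, because the documents give none of them. The gain from a better summary is real but partial: at 40 children, about 33% against 15% for a 2-SD worsening, and none for a 1-SD worsening. Severity is minor.

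**What to change.** Add to STATISTICAL ANALYSIS:

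1. Name the questionnaire as a descriptive safety outcome.
2. Pre-state a reliable-change amount, set above measurement noise and with its source given.
3. At 3 and at 6 months separately, report the number and percentage of children whose score rose, and the number and percentage whose score fell, by more than that amount since baseline, with exact 95% confidence intervals. The denominator is children with both scores; give the number missing. A child who leaves after 3 months still counts at 3 months.
4. If the sponsor adopts a cut-off, report in the same way the number who newly cross it.
5. List or plot individual changes beside the mean and SD.
6. State that a non-significant mean change will not be taken as evidence of no harm.

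The cost is a few lines and one table or figure, with no new data, visits or staff. The downside should be stated with the results: some children will be flagged by noise, worsening of about 1 SD will still usually be missed, and without a control group the count describes worsening and does not attribute it to the programme. No clinical response to individual scores is proposed here; that is for the investigators to specify.
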